5.1.2 Exclusion Criteria

Prior Therapy

- ____ 1. Anti-PD-1, anti-PD-L1, or anti-PD-L2 agents
- ____ 2. Prior radiation therapy within the field of the target lesion that in the opinion of the treating radiation oncologist would preclude further palliative radiation to a dose of 30 Gy.
- ____ 3. Anti-cancer monoclonal antibody (mAb) within 4 weeks prior to study Day 1 or who has not recovered (i.e., \leq Grade 1 or at baseline) from adverse events due to agents administered more than 4 weeks earlier.
- ____ 4. Chemotherapy, targeted small molecule therapy, or radiation therapy within 2 weeks prior to study Day 1 or who has not recovered (i.e., \leq Grade 1 or at baseline) from adverse events due to a previously administered agent.
 - Note: Subjects with \leq Grade 2 neuropathy are an exception to this criterion and may qualify for the study.
 - Note: If subject received major surgery, they must have recovered adequately from the toxicity and/or complications from the intervention prior to starting therapy.
- ____ 5. Live vaccine within 30 days of planned start of study therapy.
 - Note: Seasonal influenza vaccines for injection are generally inactivated flu vaccines and are allowed; however intranasal influenza vaccines (e.g., Flu-Mist®) are live attenuated vaccines, and are not allowed.
- ____ 6. Immunosuppressive therapy within 7 days prior to the first dose of trial treatment.

7. Investigational device within 4 weeks of the first dose of treatment

Concomitant Therapy

8. Currently receiving an investigational agent

9. About to undergo palliative radiation for a symptomatic CNS metastasis

10. Systemic steroid therapy

Other Illnesses and Conditions

11. Hypersensitivity to pembrolizumab or any of its excipients

12. Diagnosis of immunodeficiency

13. Active autoimmune disease that has required systemic treatment in the past 2 years (i.e. with use of disease modifying agents, corticosteroids or immunosuppressive drugs).

- Replacement therapy (e.g. thyroxine, insulin, or physiologic corticosteroid replacement therapy for adrenal or pituitary insufficiency, etc.) is not considered a form of systemic treatment.

14. Known history of, or any evidence of active, non-infectious pneumonitis.

15. Current active infection requiring systemic therapy

16. Known history of active TB, HIV 1/2, Hepatitis B or Hepatitis C

17. Known additional malignancy that is progressing or requires active treatment.

- Exceptions include basal cell carcinoma of the skin or squamous cell carcinoma of the skin that has undergone potentially curative therapy or in situ cervical cancer.

18. Known active central nervous system (CNS) metastases and/or carcinomatous meningitis.

- Subjects with previously treated brain metastases may participate provided they are stable (without evidence of progression by imaging for at least four weeks prior to the first dose of trial treatment and any neurologic symptoms have returned to baseline), have no evidence of new or enlarging brain metastases, and are not using steroids for at least 7 days prior to trial treatment. This exception does not include carcinomatous meningitis which is excluded regardless of clinical stability.

19. History or current evidence of any condition, therapy, or laboratory abnormality that might confound the results of the trial, interfere with the subject's participation for the full duration of the trial, or is not in the best interest of the subject to participate, in the opinion of the treating investigator.

- 20. Known psychiatric or substance abuse disorders that would interfere with cooperation with the requirements of the trial.
- 21. Pregnant or breastfeeding (female only).

5.2 Trial Treatments

The treatment to be used in this trial is outlined below in [Table 1](#).

Table 1 Trial Treatment

Drug	Dose/Potency	Dose Frequency	Route of Administration	Regimen/Treatment Period	Use
Pembrolizumab	200 mg	Q3W	IV infusion	Day 1 of each 3 week cycle	Experimental
Radiotherapy	3 Gy	Daily	External Beam	Daily except weekends and holidays for 10 fractions	Standard of care and combination agent

Trial treatment should begin as close as possible to the date on which treatment is allocated/assigned. The first dose of pembrolizumab on cycle 1, day 1 should occur on the same day after the first fraction of radiation therapy.

5.2.1 Dose Selection/Modification

5.2.1.1 Dose Selection

The rationale for selection of the dose to be used in this trial is provided in [Section 4.0 – Background and Rationale](#).

Details on preparation and administration of pembrolizumab (aka MK-3475) are provided in the Pharmacy Manual.

5.2.1.2 Dose Modification

Adverse events (both non-serious and serious) associated with pembrolizumab exposure may represent an immunologic etiology. These adverse events may occur shortly after the first dose or several months after the last dose of treatment. Pembrolizumab must be withheld for drug-related toxicities and severe or life-threatening AEs as per [Table 2](#) below. See [Section 5.4.1](#) and Events of Clinical Interest Guidance Document for supportive care guidelines, including use of corticosteroids.

Table 2: Dose Modification Guidelines for Drug-Related Adverse Event

Toxicity	Hold Treatment For Grade	Timing for Restarting Treatment	Discontinue Subject
Diarrhea/Colitis	2-3	Toxicity resolves to Grade 0-1.	Toxicity does not resolve within 12 weeks of last dose or inability to reduce corticosteroid to 10 mg or less of prednisone or equivalent per day within 12 weeks.
	4	Permanently discontinue	Permanently discontinue
AST, ALT, or Increased Bilirubin	2	Toxicity resolves to Grade 0-1	Toxicity does not resolve within 12 weeks of last dose.
	3-4	Permanently discontinue (see exception below) ¹	Permanently discontinue
Type 1 diabetes mellitus (if new onset) or Hyperglycemia	T1DM or 3-4	Hold pembrolizumab for new onset Type 1 diabetes mellitus or Grade 3-4 hyperglycemia associated with evidence of beta cell failure.	Resume pembrolizumab when patients are clinically and metabolically stable.
Hypophysitis	2-3	Toxicity resolves to Grade 0-1	Toxicity does not resolve within 12 weeks of last dose or inability to reduce corticosteroid to 10 mg or less of prednisone or equivalent per day within 12 weeks.
	4	Permanently discontinue	Permanently discontinue
Hyperthyroidism	3	Toxicity resolves to Grade 0-1	Toxicity does not resolve within 12 weeks of last dose or inability to reduce corticosteroid to 10 mg or less of prednisone or equivalent per day within 12 weeks.
	4	Permanently discontinue	Permanently discontinue
Hypothyroidism	2-4	Therapy with pembrolizumab can be continued while treatment for the thyroid disorder is instituted	Therapy with pembrolizumab can be continued while treatment for the thyroid disorder is instituted.
Infusion Reaction	3-4	Permanently discontinue	Permanently discontinue
Pneumonitis	2	Toxicity resolves to Grade 0-1	Toxicity does not resolve within 12 weeks of last dose or inability to reduce corticosteroid to 10 mg or less of prednisone or equivalent per day within 12 weeks.
	3-4	Permanently discontinue	Permanently discontinue
Renal Failure or Nephritis	2	Toxicity resolves to Grade 0-1	Toxicity does not resolve within 12 weeks of last dose or inability to reduce corticosteroid to 10 mg or less of prednisone or equivalent per day within 12 weeks.
	3-4	Permanently discontinue	Permanently discontinue
All Other Drug-Related Toxicity ²	3 or Severe	Toxicity resolves to Grade 0-1	Toxicity does not resolve within 12 weeks of last dose or inability to reduce corticosteroid to 10 mg or less of prednisone or equivalent per day within 12 weeks.
	4	Permanently discontinue	Permanently discontinue

Note: Permanently discontinue for any severe or Grade 3 drug-related AE that recurs or any life-threatening event.

¹ For patients with liver metastasis who begin treatment with Grade 2 AST or ALT, if AST or ALT increases by greater than or equal to 50% relative to baseline and lasts for at least 1 week then patients should be discontinued.

² Patients with intolerable or persistent Grade 2 drug-related AE may hold study medication at physician discretion. Permanently discontinue study drug for persistent Grade 2 adverse reactions for which treatment with study drug has been held, that do not recover to Grade 0-1 within 12 weeks of the last dose.

Dosing interruptions are permitted in the case of medical / surgical events or logistical reasons not related to study therapy (e.g., elective surgery, unrelated medical events, patient vacation, and/or holidays). Subjects should be placed back on study therapy within 3 weeks of the scheduled interruption, unless otherwise discussed with the Sponsor. The reason for interruption should be documented in the patient's study record. Dose reductions of pembrolizumab are not permitted.

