5.4 Rescue Medications & Supportive Care

5.4.1 Supportive Care Guidelines

Subjects should receive appropriate supportive care measures as deemed necessary by the treating investigator. Suggested supportive care measures for the management of adverse events with potential immunologic etiology are outlined below and in greater detail in the ECI guidance document. Where appropriate, these guidelines include the use of oral or intravenous treatment with corticosteroids as well as additional anti-inflammatory agents if symptoms do not improve with administration of corticosteroids. Note that several courses of steroid tapering may be necessary as symptoms may worsen when the steroid dose is decreased. For each disorder, attempts should be made to rule out other causes such as metastatic disease or bacterial or viral infection, which might require additional supportive care. The treatment guidelines are intended to be applied when the investigator determines the events to be related to pembrolizumab.

Note: if after the evaluation the event is determined not to be related, the investigator is instructed to follow the ECI reporting guidance but does not need to follow the treatment guidance (as outlined in the ECI guidance document). Refer to [Section 5.2.1](#) for dose modification.

It may be necessary to perform conditional procedures such as bronchoscopy, endoscopy, or skin photography as part of evaluation of the event. Suggested conditional procedures, as appropriate, can be found in the ECI guidance document.

- **Pneumonitis:**
 - For **Grade 2 events**, treat with systemic corticosteroids. When symptoms improve to Grade 1 or less, steroid taper should be started and continued over no less than 4 weeks.
 - For **Grade 3-4 events**, immediately treat with intravenous steroids. Administer additional anti-inflammatory measures, as needed.
 - Add prophylactic antibiotics for opportunistic infections in the case of prolonged steroid administration.

- **Diarrhea/Colitis:**

Subjects should be carefully monitored for signs and symptoms of enterocolitis (such as diarrhea, abdominal pain, blood or mucus in stool, with or without fever) and of bowel perforation (such as peritoneal signs and ileus).

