- All subjects who experience diarrhea/colitis should be advised to drink liberal quantities of clear fluids. If sufficient oral fluid intake is not feasible, fluid and electrolytes should be substituted via IV infusion. For Grade 2 or higher diarrhea, consider GI consultation and endoscopy to confirm or rule out colitis.
- For **Grade 2 diarrhea/colitis** that persists greater than 3 days, administer oral corticosteroids.
- For **Grade 3 or 4 diarrhea/colitis** that persists > 1 week, treat with intravenous steroids followed by high dose oral steroids.
- When symptoms improve to Grade 1 or less, steroid taper should be started and continued over no less than 4 weeks.

- **Type 1 diabetes mellitus (if new onset, including diabetic ketoacidosis [DKA]) or \geq Grade 3 Hyperglycemia, if associated with ketosis (ketonuria) or metabolic acidosis (DKA)**

- For **T1DM or Grade 3-4 Hyperglycemia**
 - Insulin replacement therapy is recommended for Type I diabetes mellitus and for Grade 3-4 hyperglycemia associated with metabolic acidosis or ketonuria.
 - Evaluate patients with serum glucose and a metabolic panel, urine ketones, glycosylated hemoglobin, and C-peptide.

- **Hypophysitis:**

- For **Grade 2** events, treat with corticosteroids. When symptoms improve to Grade 1 or less, steroid taper should be started and continued over no less than 4 weeks. Replacement of appropriate hormones may be required as the steroid dose is tapered.
- For **Grade 3-4** events, treat with an initial dose of IV corticosteroids followed by oral corticosteroids. When symptoms improve to Grade 1 or less, steroid taper should be started and continued over no less than 4 weeks. Replacement of appropriate hormones may be required as the steroid dose is tapered.

- **Hyperthyroidism or Hypothyroidism:**

Thyroid disorders can occur at any time during treatment. Monitor patients for changes in thyroid function (at the start of treatment, periodically during treatment, and as indicated based on clinical evaluation) and for clinical signs and symptoms of thyroid disorders.

- **Grade 2** hyperthyroidism events (and **Grade 2-4** hypothyroidism):

- In hyperthyroidism, non-selective beta-blockers (e.g. propranolol) are suggested as initial therapy.
- In hypothyroidism, thyroid hormone replacement therapy, with levothyroxine or liothyroinine, is indicated per standard of care.
- **Grade 3-4 hyperthyroidism**

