 - Treat with an initial dose of IV corticosteroid followed by oral corticosteroids. When symptoms improve to Grade 1 or less, steroid taper should be started and continued over no less than 4 weeks. Replacement of appropriate hormones may be required as the steroid dose is tapered.
- **Hepatic:**
 - For **Grade 2** events, monitor liver function tests more frequently until returned to baseline values (consider weekly).
 - Treat with IV or oral corticosteroids
 - For **Grade 3-4** events, treat with intravenous corticosteroids for 24 to 48 hours.
 - When symptoms improve to Grade 1 or less, a steroid taper should be started and continued over no less than 4 weeks.
- **Renal Failure or Nephritis:**
 - For **Grade 2** events, treat with corticosteroids.
 - For **Grade 3-4** events, treat with systemic corticosteroids.
 - When symptoms improve to Grade 1 or less, steroid taper should be started and continued over no less than 4 weeks.
- **Management of Infusion Reactions:** Signs and symptoms usually develop during or shortly after drug infusion and generally resolve completely within 24 hours of completion of infusion.

Table 3 below shows treatment guidelines for subjects who experience an infusion reaction associated with administration of pembrolizumab (MK-3475).

Table 3 Infusion Reaction Treatment Guidelines

NCI CTCAE Grade	Treatment	Premedication at subsequent dosing
Grade 1 Mild reaction; infusion interruption not indicated; intervention not indicated	Increase monitoring of vital signs as medically indicated until the subject is deemed medically stable in the opinion of the investigator.	None
Grade 2 Requires infusion interruption but responds promptly to symptomatic treatment (e.g., antihistamines, NSAIDS, narcotics, IV fluids);	Stop Infusion and monitor symptoms. Additional appropriate medical therapy may include but is not limited to: IV fluids Antihistamines NSAIDS	Subject may be premedicated 1.5h (\pm 30 minutes) prior to infusion of pembrolizumab (MK-3475) with:

NCI CTCAE Grade	Treatment	Premedication at subsequent dosing

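### Table 2's Grade 2 liver row lacks the steroid stopping clause that the other six resumable rows carry; secondarily, no restart cell in the protocol text states a steroid dose

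*Combined protocol and SAP*

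**What the plan says.** Table 2 in section 5.2.1.2 governs holding, restarting and stopping pembrolizumab. Seven rows share one restart condition, "Toxicity resolves to Grade 0-1". In six of these the last column ends treatment for unresolved toxicity or for "inability to reduce corticosteroid to 10 mg or less of prednisone or equivalent per day within 12 weeks". In the seventh, Grade 2 AST/ALT/bilirubin, the only stopping condition is "Toxicity does not resolve within 12 weeks of last dose".

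Section 5.4.1 lists steroid treatment for the same events. Under Grade 2 hepatic events it says "Treat with IV or oral corticosteroids". The taper instruction for pneumonitis, repeated in near-identical words for the other named toxicities, is: "When symptoms improve to Grade 1 or less, steroid taper should be started and continued over no less than 4 weeks". The section also warns that "several courses of steroid tapering may be necessary as symptoms may worsen when the steroid dose is decreased".

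The lead-in to Table 2 sends the reader to section 5.4.1 and to the "Events of Clinical Interest Guidance Document for supportive care guidelines, including use of corticosteroids". Appendix 3 identifies the version of that guidance (5.0) but does not reproduce its text.

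**The concern.** The main issue is an unexplained inconsistency between rows. Steroid dependence at 12 weeks ends treatment after colitis, pneumonitis or nephritis, but not after Grade 2 hepatitis, for which the protocol also lists steroids. Such a patient could stay on a checkpoint inhibitor with liver tests held down by more than 10 mg of prednisone a day.

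The secondary issue is timing. A patient who is at Grade 0-1 because of steroids satisfies the restart cell on the day the taper begins. Read literally, the table allows re-dosing early in the taper, when a flare could be masked or treated late. This matters most for pneumonitis, hypophysitis, hyperthyroidism and persistent colitis. It matters less for liver events and, at least partly, for renal events, because the chemistry panel (which includes AST, ALT, bilirubin and blood urea nitrogen) is reviewed before each dose.

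**Working it through.** The plan gives no figure to reproduce, so the check is a row count, a trace of one patient through the rules, and a comparison of two intervals.

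**1. Row count (Table 2 against section 5.4.1).** Every row below restarts at Grade 0-1.

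| Row (grade held) | Steroid dose in restart cell | 10 mg / 12-week stopping clause | Steroids in 5.4.1 | Taper in 5.4.1 |
|---|---|---|---|---|
| Diarrhea/colitis (2-3) | none | yes | only if persistent: over 3 days (Grade 2), over 1 week (Grade 3) | at least 4 weeks |
| AST/ALT/bilirubin (2) | none | **no** | yes | at least 4 weeks |
| Hypophysitis (2-3) | none | yes | yes | at least 4 weeks |
| Hyperthyroidism (3) | none | yes | yes | at least 4 weeks |
| Pneumonitis (2) | none | yes | yes | at least 4 weeks |
| Renal failure/nephritis (2) | none | yes | yes | at least 4 weeks |
| All other (3 or severe) | none | yes | no rule | no rule |

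Restart cells with a steroid dose: 0 of 7. Rows with the steroid stopping clause: 6 of 7. The diabetes/hyperglycemia and hypothyroidism rows use different restart logic and are not counted.

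**2. Trace of a liver patient.** Suppose a Grade 2 hepatic event is treated with steroids, improves to Grade 0-1 within 12 weeks, and still needs more than 10 mg/day at 12 weeks.
- Liver row: toxicity has resolved, so the row does not stop treatment.
- Footnote 1 covers patients with liver metastasis who start with Grade 2 AST or ALT and then rise by at least 50%. It does not apply here.
- The note under the table covers recurrent Grade 3 or severe events and life-threatening events. It does not apply.
- Section 5.6 refers back to 5.2.1.2 for toxicity and otherwise leaves the investigator's decision.
- Section 5.3 carries the steroid exclusion (criterion 10) into the trial, but 5.3.2 exempts steroids for immune-related events without a dose limit.
- Section 7.1.3 requires acceptable laboratory results and names no steroid dose. Section 7.1.1.7 requires consultation only for gaps over 12 weeks.

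No rule stops the patient. In any of the other six rows the same steroid need would.

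**3. Taper against dosing interval.** Inputs: 21-day cycle (Table 1), ±3-day window (5.2.2), minimum taper 4 × 7 = 28 days (5.4.1). If the taper starts on the day Grade 0-1 is reached, the next scheduled slot lies d = 0 to 20 days later.
- Latest next slot: 20 days, or 20 + 3 = 23 with the window. Both are below 28, so the next slot falls inside the minimum taper at every schedule position.
- Second slot: d + 21 < 28 holds for d = 0 to 6, which is 7 of 21 positions (4 if given 3 days late, 10 if 3 days early).

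This step needs no assumption about steroid dose.

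**4. Illustration only.** The documents give no starting dose or taper shape. Assume a linear taper from S mg over 28 days. Days above 10 mg = 28 × (1 − 10/S).

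| S (mg) | Days above 10 mg | Next slot above 10 mg, of 21 (no window) | Doses delayed if 10 mg were required |
|---|---|---|---|
| 20 | 14.0 | 14 | 0 in 7, 1 in 14 |
| 40 | 21.0 | 21 | 1 in 21 |
| 60 | 23.3 | 21 | 1 in 18, 2 in 3 |
| 80 | 24.5 | 21 | 1 in 17, 2 in 4 |

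With a 56-day taper from 60 mg, the time above 10 mg is 56 × (1 − 10/60) = 46.7 days. The delay is then 2 doses in 16 positions and 3 in 5.

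**The case against.** The strongest reply concerns the restart cells. Table 2 points to external guidance for corticosteroid use, and section 5.4.1 describes itself as an outline of it. That guidance may state a restart dose. The hold-restart-discontinue layout also suggests that the drug is meant to stay on hold until steroids reach 10 mg; otherwise a 12-week limit on reaching 10 mg serves little purpose. Restart is permitted, not required. This is one institution with one principal investigator grading and attributing events, so differing readings across sites are not an issue.

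Most of that stands. A reader might infer that the plan has no steroid ceiling at all, or that it directs re-dosing on high-dose steroids in all seven rows. The documents support neither. The guidance is unseen, the wording is permissive, the all-other row has no taper rule, and colitis gets steroids only if it persists (for Grade 2, "that persists greater than 3 days, administer oral corticosteroids"). What remains is that the table does not state the ceiling where the restart decision is made.

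On the liver row, the reply is that it is otherwise strict. Grade 3 means permanent discontinuation, a return to Grade 2 triggers another hold, laboratory results must be acceptable at each dose, and the investigator may withdraw the patient. These protections make harm less likely, but they do not supply the missing clause or explain why it is missing. This part does not depend on how the restart cells are read.

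**Conclusion.** The point holds at minor, safety-wording priority. The firm part is the liver row: it is the only one of seven resumable rows without the 10 mg / 12-week stopping clause, and a steroid-dependent patient at Grade 0-1 meets no Table 2 stopping rule. The restart part is conditional. For the six named toxicities, when steroids are given, the protocol text lets the next scheduled dose fall inside the taper and sets no steroid ceiling, subject to what the unreproduced guidance says and to the ceiling that the 12-week clause may imply.

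The milligram and delay figures rest on an assumed linear taper from 20 to 80 mg and should not be read as properties of the plan. The number of affected patients is not given and is likely small among 14. No endpoint, power or alpha figure is affected.

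**What to change.** 1. Add to the Grade 2 AST/ALT/bilirubin row the steroid stopping clause that the other six rows carry.
2. In the seven restart cells, add that if corticosteroids were given, the daily dose must be no more than 10 mg in prednisone equivalents. If the Events of Clinical Interest guidance already says this, cite it in those cells instead.
3. State the date from which the 12 weeks in the steroid clause run. The text ties the last dose only to toxicity resolution.

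The cost is amendment wording in one table, with no extra visits, patients or data. Restart would be delayed, typically by about one or two doses under the assumed tapers, and longer with slow or repeated tapers. A rare patient with steroid-dependent Grade 2 hepatitis would be discontinued. The anchor date matters: if the 12 weeks run from the last dose (an assumption), a patient starting at 60 mg must reach Grade 0-1 by about day 84 − 23.3 = 60.7 with a 28-day taper, or day 84 − 46.7 = 37.3 with a 56-day taper, to be at 10 mg in time.

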8.3 Adverse Events and Serious Adverse Events

The PI will be responsible for determining the event name, assessing the severity (i.e., grade), expectedness, and attribution of all adverse events.

Adverse Event (AE) - An adverse event is any untoward medical experience or change of an existing condition that occurs during or after treatment, whether or not it is considered to be related to the protocol intervention.

Reporting Non-serious Adverse Events – Adverse events will be collected after the patient is given the study treatment or any study related procedures. Adverse events will be monitored by the PMT. Adverse events that do not meet the criteria of serious OR are not unanticipated problems will be reported only in the PMT Report.

Serious Adverse Event (SAE) [Modified from the definition of unexpected adverse drug experience in [21 CFR 312.32](#)] - defined as *any expected or unexpected adverse events* that result in any of the following outcomes:

- Death
- Is life-threatening experience (places the subject at immediate risk of death from the event as it occurred)
- Unplanned hospitalization (equal to or greater than 24 hours) or prolongation of existing hospitalization
- A persistent or significant disability/incapacity
- A congenital anomaly/birth defect
- Secondary malignancy
- Any other adverse event that, based upon appropriate medical judgment, may jeopardize the subject's health and may require medical or surgical intervention to prevent one of the outcomes listed above (examples of such events include allergic bronchospasm requiring intensive treatment in the emergency room or at home, blood dyscrasias or convulsions that do not result in inpatient hospitalization, or the development of drug dependency or drug abuse).

Reporting Serious Adverse Events - begins after study treatment or any study related procedures. All SAEs occurring during this study, whether observed by the physician, nurse, or reported by the patient, will be reported according to the approved [City of Hope's Institutional policy](#) [policy effective date: 05/14/14]. Serious Adverse Events that require expedited reporting will be submitted electronically using [iRIS](#).

Adverse Event Name and Severity

The PI will determine the adverse event name and severity (grade) by using the CTCAE version 4.0.

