9.2 Secondary Objectives

Secondary objectives such as ORR per RECIST 1.1 and irRECIST, PFS, and OS are exploratory, though will also be documented, along with toxicity. All patients who receive at least one dose of pembrolizumab will be included in the safety analysis. Stool/oral microbiomic profiling and germline miRNA biomarker panel analyses will also be correlated with secondary outcome measures of ORR and toxicities.

While overlapping toxicities are not anticipated with the combination of pembrolizumab and RT, the initial treatment of patients within this trial warrants a careful review of toxicity:

- **Toxicity-based Interim Analysis:** A study hold will be placed for re-evaluation at the proposed starting dose as accrual proceeds on this phase II study according to the following rule: The study will hold pending an amendment if 3 patients discontinue therapy after cycle 1 due to treatment-related toxicity. This rule has a 97% chance of holding the study if the true discontinuation rate due to toxicity on cycle 1 is 50%. It has a 15% chance of holding if the true discontinuation rate on cycle 1 is 15%.
- **Treatment-related mortality stopping rule:** Any treatment-related death will hold the study accrual pending review by the PI, Sponsor, and DSMB/IRB.

With 14 patients, there is 96% power to detect at least one responder if the true response rate is 21% or higher, which is in the range of 22% in the phase I trial of pembrolizumab among gastric cancer patients with PD-L1 overexpression. As a result, failure to observe any response in the 14 patients would result in lack of enthusiasm for the combination of pembrolizumab and RT in this patient population. PFS and OS will be determined using the Kaplan-Meier method.

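### Table 2's Note requires a permanent stop for any life-threatening event, but the hypothyroidism and diabetes/hyperglycemia rows lead to continued or resumed pembrolizumab, and nothing says which text governs

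*Combined protocol and SAP*

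**What the plan says.** Section 5.2.1.2 introduces Table 2 with a general requirement: "Pembrolizumab must be withheld for drug-related toxicities and severe or life-threatening AEs as per" the table. Four pieces of text then bear on the point.

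- **Note under the table:** "Permanently discontinue for any severe or Grade 3 drug-related AE that recurs or any life-threatening event". It names no row as exempt.
- **Hypothyroidism row, Grades 2-4:** "Therapy with pembrolizumab can be continued while treatment for the thyroid disorder is instituted". Grade 4 has no line of its own.
- **Type 1 diabetes/hyperglycemia row, T1DM or Grades 3-4:** "Hold pembrolizumab for new onset Type 1 diabetes mellitus or Grade 3-4 hyperglycemia associated with evidence of beta cell failure", followed by "Resume pembrolizumab when patients are clinically and metabolically stable". Grade 4 again has no separate line.
- **Section 5.6:** adverse experiences that are unacceptable under Section 5.2.1.2 are among the reasons for which a subject must be discontinued.

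On severity, Section 8.3 says "The PI will determine the adverse event name and severity (grade) by using the CTCAE version 4.0", but the grade definitions are not printed. The only wording in the documents that explains the term life-threatening is in the list of serious adverse event criteria in the same section. It turns on immediate risk of death from the event as it occurred and is not tied to a grade.

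**The concern.** Table 2 is the text a treating physician consults to decide whether a patient stays on pembrolizumab, and Section 5.6 makes it the reference for a compulsory stop. For a life-threatening event in either endocrine row, the row keeps the patient on drug or returns the patient to it, while the Note ends treatment for good. Two physicians following the protocol faithfully could reach different end results for the same event. Whichever they chose, a monitor could cite the other line as a deviation. The stake is chiefly patient management, and after that the consistency of the recorded reasons for discontinuation.

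**Working it through.** No figure in the plan is involved and no arithmetic applies beyond counting rows. The check sets the texts side by side.

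**Step 1. What each row says at Grade 4.**

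| Table 2 row | End result at Grade 4 | Agrees with the Note? |
|---|---|---|
| Diarrhea/colitis | Permanent stop | Yes |
| AST, ALT or bilirubin | Permanent stop (Grades 3-4), with a flagged exception in footnote 1 | Yes |
| T1DM/hyperglycemia | Hold, then resume when stable | **No** |
| Hypophysitis | Permanent stop | Yes |
| Hyperthyroidism | Permanent stop | Yes |
| Hypothyroidism | May continue | **No** |
| Infusion reaction | Permanent stop (Grades 3-4) | Yes |
| Pneumonitis | Permanent stop (Grades 3-4) | Yes |
| Renal failure/nephritis | Permanent stop (Grades 3-4) | Yes |
| All other drug-related toxicity | Permanent stop | Yes |

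Eight rows agree with the Note and two do not: 10 - 8 = 2.

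**Step 2. Whether anything exempts those two rows.** Footnote 1 belongs to the liver row and footnote 2 to the all-other row. Neither mentions thyroid disease or diabetes. The liver row points the reader to its exception, so the table has a way of marking one, and neither endocrine row uses it.

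**Step 3. Whether another section settles precedence.** The lead-in sentence defers to the table. Section 5.4.1 gives hormone replacement for hypothyroidism and insulin for diabetes, but sends the reader back to Section 5.2.1 for dose modification. Section 5.6 also points back to Section 5.2.1.2. No sentence ranks the rows against the Note.

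**Step 4. Which events are caught.** This depends on what life-threatening means in the Note.

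- *If Grade 4 is taken as life-threatening:* every Grade 4 hypothyroidism, and every Grade 4 hyperglycemia with evidence of beta cell failure. This is an assumption. The table is compatible with it, since the last row pairs Grade 3 with severe and lists Grade 4 separately with a permanent stop.
- *If the Section 8.3 criterion is used:* only those events in the two rows that put the patient at immediate risk of death. The set is smaller but not empty in principle. Section 5.4.1 places diabetic ketoacidosis under its new-onset diabetes heading, and whether a given case meets the criterion is for the investigator to judge.

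On either reading the Note and the row give different end results for at least some events.

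**The case against.** The best reply is that specific text overrides general text. The hypothyroidism row names Grade 4 expressly, and Section 5.4.1 groups Grades 2-4 hypothyroidism together under hormone replacement and provides insulin for the diabetic events. These entries look deliberate. This may well be what was meant, but the document does not say so, and a Note worded to cover any such event reads naturally as applying to the whole table.

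The row wording also limits the conflict. The hypothyroidism entry is permissive, and the hyperglycemia entry requires a hold first and evidence of beta cell failure. The disagreement is therefore about the end result, not about whether to interrupt. The study is small and run at one institution, with the principal investigator responsible for grading and attribution, which limits how differently the table could be read in practice.

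A reader might infer more than the text supports:

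- **Three rival instructions (hold, continue, stop).** The column headed for holding also lists grades whose instruction is a permanent stop, so it works as an index of grades. Hold and resume are consecutive steps.
- **A clash over recurrent Grade 3 events.** Several other rows also allow restart after Grade 3, and the Note adds the recurrence rule to them all. That is how the table is built.
- **Text in the wrong columns.** The table was read from a PDF, and cell placement may have shifted.
- **A material effect on the Section 9.2 hold rule.** The rule reads "The study will hold pending an amendment if 3 patients discontinue therapy after cycle 1 due to treatment-related toxicity", so a discontinuation could in principle be counted. Its stated properties, however, concern discontinuation on cycle 1, and the study calendar schedules thyroid tests at screening and then on day 1 of even-numbered cycles. The first scheduled on-study result is therefore at cycle 2, day 1. With no event rate in the documents, no size can be put on this link.

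**Conclusion.** The contradiction is real but narrow. In two of ten rows, an event that is life-threatening has one end result under the row and another under the Note, and the documents do not rank them. The conflict extends to all Grade 4 events in those rows only on the assumption that Grade 4 means life-threatening. Without it, the conflict is confined to events meeting the Section 8.3 criterion. The number of patients affected cannot be estimated, and among 14 it may be none. The point should still be corrected, because Section 5.6 makes this text the basis for a mandatory stop and the consequence for an affected patient is large. It does not bear on the sample size or the primary analysis.

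**What to change.** Amend Table 2 so that the Note and the two endocrine rows give one instruction for each event, and state which text governs where a row and the Note both apply. Define life-threatening for the purpose of the Note, by CTCAE grade or by the Section 8.3 criterion, so that its scope is clear. Which instruction should apply is a clinical decision for the sponsor and investigator, and no view on it is offered here. The cost is a few lines of wording in an amendment, with no added procedure, visit or patient.
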